2.4 IMMUNOGENICITY OBJECTIVE

The immunogenicity objective for this study is to evaluate the immune response to atezolizumab and Hu5F9-G4 on the basis of the following endpoints:

- Incidence of ADAs against atezolizumab during the study relative to the prevalence of ADAs at baseline
- Incidence of ADAs against Hu5F9-G4 during the study relative to the prevalence of ADAs at baseline

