- Hu5F9-G4 will be given as two priming doses of 1 mg/kg IV on Days 1 and 4, followed by loading doses of 10 mg/kg IV on Day 8 and 15 mg/kg on Day 11. Starting on Day 15, maintenance treatment with Hu5F9-G4 will be given by IV infusion at a dose of 15 mg/kg QW.
- If $<33\%$ (i.e., 1 or fewer of 6 patients) *patients in the de-escalation cohort experience a DLT*, an expansion cohort of 9 patients will be enrolled to further test the safety and anti-tumor activity of atezolizumab in combination with Hu5F9-G4, using the same dosing regimen

If DLTs are observed in $<33\%$ of patients (i.e., 1 or fewer of 6 patients) in the initial safety cohort, an expansion cohort of 15 patients will be enrolled to further test the safety and anti-tumor activity of atezolizumab in combination with Hu5F9-G4, using the same dosing regimen.

Study treatment will be administered until unacceptable toxicity or loss of clinical benefit, as determined by the investigator, after local biopsy results (if available) and clinical status (e.g., symptomatic deterioration such as pain secondary to disease) are assessed.

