Between 10% and 40% of newly diagnosed patients with AML do not achieve CR with intensive induction therapy and are therefore categorized as having disease that is primary refractory or resistant. In addition, between 30% and 80% of patients who achieve a CR will subsequently relapse. Few of these patients can be cured with conventional salvage therapy (Thol et al. 2015). Most patients with R/R AML should be enrolled in clinical trials, given that highly effective and standardized treatments for AML are lacking and clinical trial enrollment is encouraged in this population.

3.3.4 **Rationale for Hu5F9-G4 Dose**

The dosing schedule chosen for Hu5F9-G4 was established during the Phase I clinical trial, during which no MTD was identified at doses of up to 30 mg/kg twice a week. In addition, PD assessments, conducted during the same Phase I clinical trial demonstrated that a priming dose for the first week, followed by escalating doses during the second week, and subsequently by weekly doses of the anti-CD47 monoclonal antibody, was not associated with early deaths, was safe and well tolerated in AML patients, resulted in a linear PK profile (see [Figure 2](#)), and optimal CD47 antigen binding in bone marrow at steady state (see [Figure 2](#)).

Figure 2 Hu5F9-G4 Achieves Target PK Levels at Clinically Feasible Doses

- 5F9 can overcome the CD47 antigen sink at 10 mg/kg or higher
- Antibody half-life is ~13 days
- Free plasma drug levels exceed preclinical activity thresholds identified from PK modeling (>100 to 250 μg/ml)

5F9 = Hu5F9-G4; PK = pharmacokinetic.

Source: Agoram et al. 2018.

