4.5.10 Anti-Drug Antibody Testing

Atezolizumab may elicit an immune response. Patients with signs of any potential immune response to atezolizumab will be closely monitored. Validated screening, confirmatory, and titer assays will be employed to detect ADAs at multiple timepoints before, during, and after treatment with atezolizumab and Hu5F9-G4 (see [Appendix 2](#) for the schedule of ADA assessments). ADA response will be correlated with relevant clinical endpoints to understand its clinical significance. Additional ADA assays (e.g., neutralizing antibody assay) may be employed to further characterize ADA response.

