- w Two priming doses of 1 mg/kg of Hu5F9-G4 will be administered to patients by continuous IV infusion on Days 1 and 4 of Cycle 1, followed by loading doses of 15 mg/kg on Day 8 and 30 mg/kg on Day 11. Starting on Day 15 of Cycle 1, Hu5F9-G4 maintenance will be given at a dose of 30 mg/kg QW of each 28-day cycle.
- x Atezolizumab will be administered to patients by IV infusion at a fixed dose of 840 mg, starting on Day 22 of Cycle 1. In subsequent cycles, 840 mg of atezolizumab will be given Q2W on Days 8 and 22 of each 28-day cycle. The initial infusion of atezolizumab will be delivered over 60 (\pm 15) minutes. Subsequent infusions will be delivered over 30 (\pm 10) minutes if the previous infusion was tolerated without infusion-associated adverse events, or 60 (\pm 15) minutes if the patient experienced an infusion-associated adverse event with the previous infusion. *For the first two doses of atezolizumab following Hu5F9-G4, at least 60 minutes should be allowed for observation after Hu5F9-G4 administration and 60 minutes for observation after atezolizumab administration. If no infusion-associated adverse events are observed during the initial two combination treatment sessions, a 30-minute observation period between Hu5F9-G4 and atezolizumab infusion and a 30-minute observation period after atezolizumab infusion could be considered for subsequent administrations.*

Appendix 1

Schedule of Activities (cont.)

- ✓ After treatment discontinuation, information on survival follow-up and new anti-cancer therapy (including targeted therapy and immunotherapy) will be collected via telephone calls, patient medical records, and/or clinic visits approximately every 3 months (unless the patient withdraws consent or the Sponsor terminates the study). If a patient requests to be withdrawn from follow-up, this request must be documented in the source documents and signed by the investigator. If the patient withdraws from the study, the study staff may use a public information source (e.g., county records) to obtain information about survival status only.

Appendix 2

Schedule of Pharmacokinetic and Immunogenicity Samples

Visit	Timepoint(s)	Sample Type
Cycle 1, Day 1	Prior to the first infusion of Hu5F9-G4	
 • Hu5F9-G4 PK (serum) • Hu5F9-G4 ADA (serum)
	1 hour (\pm 15 minutes) after the end of the infusion of Hu5F9-G4	
 • Hu5F9-G4 PK (serum)

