Cycle 7, Day 1	Prior to the first infusion	
 • Hu5F9-G4 PK (serum)
Cycle 8, Day 22	Prior to the first infusion	
 • Atezolizumab PK (serum) • Atezolizumab ADA (serum)

ADA=anti-drug antibody; PK=pharmacokinetic.

Note: Except for Day 1 of Cycle 1, all other study visits and assessments during the treatment period should be performed within \pm 3 days of the scheduled date. Study assessments may be delayed or moved ahead of the window to accommodate holidays, vacations, and unforeseen delays.

Appendix 2
Schedule of Pharmacokinetic and Immunogenicity Samples
(cont.)

Visit	Timepoint(s)	Sample Type
Cycle 9, Day 1	Prior to the first infusion	
 • Hu5F9-G4 PK (serum)
Cycle 11, Day 1	Prior to the first infusion	
 • Hu5F9-G4 PK (serum) • Hu5F9-G4 ADA (serum)
Cycle 12, Day 22	Prior to the first infusion	
 • Atezolizumab PK (serum) • Atezolizumab ADA (serum)
Cycle 13, Day 1	Prior to the first infusion	
 • Hu5F9-G4 PK (serum)
Cycle 15, Day 1	Prior to the first infusion	
 • Hu5F9-G4 PK (serum) • Hu5F9-G4 ADA (serum)
Cycle 16, Day 22	Prior to the first infusion	
 • Atezolizumab PK (serum) • Atezolizumab ADA (serum)
Cycle 17, Day 1, and Day 1 of every 2 cycles thereafter	Prior to the first infusion	
 • Hu5F9-G4 PK (serum)
Treatment discontinuation visit (≤ 30 days after final dose)	At visit	
 • Atezolizumab PK (serum) • Hu5F9-G4 PK (serum) • Atezolizumab ADA (serum) • Hu5F9-G4 ADA (serum)
120 ± 30 days after final dose of atezolizumab	At visit	
 • Atezolizumab PK (serum) • Atezolizumab ADA (serum)

ADA=anti-drug antibody; PK=pharmacokinetic.

Note: Except for Day 1 of Cycle 1, all other study visits and assessments during the treatment period should be performed within ± 3 days of the scheduled date. Study assessments may be delayed or moved ahead of the window to accommodate holidays, vacations, and unforeseen delays.

Appendix 3

Schedule of Biomarker Samples

Sample Type	Screening	Treatment				At Time of Relapse, PD, or Suspected PD ^{a, b}	Study Tx Discon ^c	Unscheduled Visit ^c	Survival Follow-Up ^d
		Cycle 1		Cycle 2	Cycle 4				
	Days -28 to -1	Day 1	Day 22	Day 15	Day 1	NA	NA	NA	

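### Hu5F9-G4 anti-drug antibody has no planned washout sample when both drugs stop together, and a negative result counts as negative whatever the drug level, so incidence may be understated

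*Combined protocol and SAP*

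**What the plan says.** Section 2.4 lists as an endpoint "Incidence of ADAs against Hu5F9-G4 during the study relative to the prevalence of ADAs at baseline". Section 4.5.10 says that validated assays will "detect ADAs at multiple timepoints before, during, and after treatment with atezolizumab and Hu5F9-G4".

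Appendix 2 schedules Hu5F9-G4 ADA before dosing on Day 1 of Cycles 1 (baseline), 2, 3, 5, 11 and 15, and at the discontinuation visit, which falls within 30 days of the final dose. Each of these has a Hu5F9-G4 concentration sample at the same timepoint. One further serum draw is planned, "120 ± 30 days after final dose of atezolizumab", for atezolizumab concentration and atezolizumab ADA only.

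On exposure, Figure 2 in Section 3.3.4 states "Antibody half-life is ~13 days" and reports free drug above activity thresholds of 100 to 250 µg/mL. In the initial regimen (Appendix 1, note w), "maintenance will be given at a dose of 30 mg/kg QW of each 28-day cycle". In the de-escalation cohort (Section 3.1.1), "maintenance treatment with Hu5F9-G4 will be given by IV infusion at a dose of 15 mg/kg QW".

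Section 6.7 classes a patient who is negative or missing at baseline as ADA negative if every postbaseline sample is negative. Drug concentration plays no part in that rule. Section 6.7 then relates ADA status to safety, efficacy, PK and biomarker endpoints.

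**The concern.** Circulating drug can compete with an ADA immunoassay and hide antibody. The error runs one way: a masked positive is read as a negative. If a patient's postbaseline samples are all taken with a lot of drug present, and the rule calls every such negative a true negative, the reported incidence can only be pulled down. The planned comparisons by ADA status would then mix masked positives with true negatives. With at most 21 patients, a few such cases would visibly change the rate.

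The schedule treats the two drugs differently. Atezolizumab gets a late sample and Hu5F9-G4 does not, and no reason is given, although the late serum is drawn anyway.

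**Working it through.** **Inputs from the documents.** Half-life 13 days (Section 3.3.4, Figure 2). Dosing of 1, 1, 15, 30, then 30 mg/kg weekly from Day 15; de-escalation cohort 1, 1, 10, 15, then 15 mg/kg weekly (Section 3.1.1). Sampling times from Appendix 2.

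**Assumed.** One-compartment linear kinetics and a volume of distribution V of 40 to 100 mL/kg. The documents give no volume, so their exposure statement can be checked for consistency but not reproduced.

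**Drug remaining t days after the last dose**, fraction = 0.5^(t/13):

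| Days | Half-lives | Remaining |
|---|---|---|
| 30 | 2.3 | 20% |
| 90 | 6.9 | 0.82% |
| 120 | 9.2 | 0.17% |
| 150 | 11.5 | 0.03% |

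**On-treatment predose level.** With f = 0.5^(7/13) = 0.6885, the steady-state trough is (dose/V) × f/(1 − f) = (dose/V) × 2.21.
- 30 mg/kg: dose/V is 300 to 750 µg/mL, so the trough is 663 to 1,658 µg/mL. Summing the doses given by Cycle 2 Day 1, before steady state, gives 518 to 1,294. The range over the scheduled draws is about 520 to 1,660.
- 15 mg/kg: trough 332 to 829; Cycle 2 Day 1 from 269. The range is about 270 to 830.

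These values are consistent with the stated floor of 100 to 250 µg/mL.

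**Discontinuation visit at its latest, day 30, after steady-state dosing.** Peak = (dose/V)/(1 − f) = (dose/V) × 3.21; multiply by 0.202.
- 30 mg/kg: 194 to 486 µg/mL.
- 15 mg/kg: 97 to 243 µg/mL.
- Using only the document's floor as a 7-day trough: 100 to 250 × 0.5^(23/13) = 29 to 73 µg/mL.

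Day 30 is the latest case. Appendix 1, note a, lets the visit showing progression serve as the discontinuation visit, so the last sample may come sooner and hold more drug.

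**Late draw, counted from the last Hu5F9-G4 dose at 30 mg/kg.** Day 90: 7.9 to 19.8 µg/mL. Day 120: 1.6 to 4.0. Day 150: 0.3 to 0.8.

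**Sensitivity of the late draw.**
- From day 30 to day 90 the fall is 2^(60/13) = 24-fold, or 2^(60/16) = 13-fold if the half-life were 16 days. With a 16-day half-life and V = 40 mL/kg, about 780 µg/mL at day 30 becomes about 58 at day 90.
- The draw is timed from atezolizumab. If the last Hu5F9-G4 dose comes 14 days later, the earliest draw is 76 days after it: 0.5^(76/13) = 1.7% remaining.
- After a 12-week atezolizumab hold with Hu5F9-G4 continuing, day 120 could be 120 − 84 = 36 days after the last Hu5F9-G4 dose: 0.5^(36/13) = 15% remaining.

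**The case against.** The strongest objection is that the deciding quantity is missing. Masking depends on the assay's drug tolerance, and Sections 4.5.7.2 and 4.5.10 say only that the assays are validated. A reader might infer that incidence is probably biased low. The documents do not support that; they support only that it may be, depending on tolerance.

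A reader might also infer that all postbaseline samples hold hundreds of µg/mL and that no patient is ever sampled after washout. Neither holds:
- A patient who stops after the two priming doses would be at about 4 to 9 µg/mL at day 30, and one who stops after the Day 8 dose of 15 mg/kg at about 33 to 83. Figure 2 adds that "5F9 can overcome the CD47 antigen sink at 10 mg/kg or higher", so linear kinetics may overstate levels after priming.
- Appendix 8 allows atezolizumab to continue after Hu5F9-G4 stops, so later Hu5F9-G4 ADA draws can fall after washout.

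Nor does the schedule contradict Section 4.5.10. The discontinuation-visit sample is literally after treatment, and that section does not promise a washout sample.

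The plan also has partial safeguards. Every Hu5F9-G4 ADA sample has a paired concentration, serum may be kept for up to five years after the study report for further immunogenicity work (Section 4.5.7.2), and additional ADA assays are allowed. The endpoint is descriptive, and no dose, stopping or efficacy decision uses ADA status.

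All of this stands and limits how much the point matters. It does not supply a late sample for a patient who stops both drugs together, and having paired concentrations does not help while Section 6.7 makes no use of them.

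**Conclusion.** The gap is real and narrow. For a patient who stops both drugs together, the last Hu5F9-G4 ADA sample comes at most 2.3 half-lives after the final dose, with about 20% or more of the drug remaining. On-treatment samples under continuous weekly dosing hold several hundred µg/mL or more. A negative under those conditions counts as a true negative. Incidence may therefore be understated unless the assay tolerates several hundred µg/mL or more.

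The half-lives and percentages rest on the protocol's own 13 days. The concentrations rest also on the assumed volume and linear kinetics. The size of any understatement cannot be computed, because neither the tolerance nor the true ADA rate is given. It would also go too far to infer that the late sample is certain to be free of interference: at day 90 with a longer half-life, or after a long atezolizumab hold, appreciable drug could remain. This is a cheap improvement to a descriptive endpoint and does not threaten the trial's main conclusions.

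**What to change.** 1. In Appendix 2, add Hu5F9-G4 ADA and a paired Hu5F9-G4 concentration to the existing draw at 120 ± 30 days, and record the time since the last Hu5F9-G4 dose, because that draw is timed from atezolizumab.
2. In Section 6.7, state the assay's validated drug tolerance. Report a negative sample whose paired Hu5F9-G4 concentration exceeds it as inconclusive rather than negative.

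Running the ADA assay on the Hu5F9-G4 serum already drawn at Cycles 7, 9 and 13 would not help with masking, since those are predose samples during weekly maintenance.

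The cost is a few extra assays on a draw already planned, with no added visit. Only patients who reach that visit benefit, and eligibility requires a life expectancy of just 12 weeks, so attendance may be limited. Fewer patients may end up classed as ADA negative. The inconclusive category works even without the late sample, because the paired concentrations are already collected.

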Appendix 7 **Anaphylaxis Precautions**

EQUIPMENT NEEDED

- Oxygen
- Epinephrine for subcutaneous, intravenous, and/or endotracheal use in accordance with standard practice
- Antihistamines
- Corticosteroids
- Intravenous infusion solutions, tubing, catheters, and tape

PROCEDURES

In the event of a suspected anaphylactic reaction during study treatment infusion, the following procedures should be performed:

1. Stop the study treatment infusion.
2. Maintain an adequate airway.
3. Administer antihistamines, epinephrine, or other medications as required by patient status and directed by the physician in charge.
4. Continue to observe the patient and document observations.

Appendix 8

Overall Guidelines for Management of Patients Who Experience Adverse Events

DOSE MODIFICATIONS

There will be no dose modifications for atezolizumab in this study. The dose of Hu5F9-G4 may be decreased to 20 mg/kg after consultation with the Medical Monitor.

In general, Hu5F9-G4 dose reductions to 20 mg/kg may be considered for Hu5F9-G4-related toxicities that are Grade 3 or 4; however, the following are generally not reasons for dose reduction:

- Grade 3 anemia: Grade 3 hemolytic anemia that is medically significant, requiring hospitalization or prolongation of existing hospitalization, disabling or limiting self-care activities of daily life, may result in dose reduction
- Grade 3 indirect or unconjugated hyperbilirubinemia that resolves to Grade ≤ 2 with supportive care within 7 days and is not associated with other clinically significant sequelae
- Grade 3 elevation in ALT, AST, or ALP that resolves to Grade ≤ 2 with supportive care within 1 week and is not associated with other clinically significant sequelae
- Transient Grade 3 nausea, vomiting, diarrhea, local reactions, influenza-like symptoms, myalgias, fever, headache, pain during the infusion, or skin toxicity that resolves to Grade ≤ 2 within ≤ 72 hours after medical management (e.g., supportive care, including immunosuppressant treatment) has been initiated
- Grade 3 fatigue that resolves to Grade ≤ 2 within 2 weeks of Day 1 of the next cycle of study treatment
- Grade 3 Hu5F9-G4-related infusion reactions in the absence of an optimal pretreatment regimen, which is defined as acetaminophen or a comparable non-steroidal anti-inflammatory agent, plus an antihistamine and corticosteroids
- Grade 3 tumor lysis syndrome or electrolyte disturbances (hyperkalemia, hypophosphatemia, hyperuricemia, etc.) that resolve to Grade ≤ 2 or baseline value within 7 days
- Grade 3 or 4 lymphopenia or leukopenia
- Any Grade 3 autoimmune toxicity that clinically resolves to Grade ≤ 2 within 7 days of initiating therapy
- Grade 3 diarrhea or skin toxicity that resolves to Grade 1 or better in <7 days after medical management (e.g., immunosuppressant treatment) has been initiated
- Other single laboratory values out of normal range that have no clinical correlate and resolve to Grade ≤ 2 or to baseline within 7 days with adequate medical management
- Tumor flare phenomenon defined as local pain, irritation, or rash localized at sites

Appendix 8

Overall Guidelines for Management of Patients Who Experience Adverse Events (cont.)

Patients who are deemed to require further dose reductions <20 mg/kg of Hu5F9-G4 should be discontinued from study treatment with Hu5F9-G4.

TREATMENT INTERRUPTION

Atezolizumab treatment may be temporarily suspended in patients experiencing toxicity considered to be related to study treatment. If corticosteroids are initiated for treatment of the toxicity, they must be tapered over ≥ 1 month to the equivalent of ≤ 10 mg/day oral prednisone before atezolizumab can be resumed. If atezolizumab is withheld for > 12 weeks after event onset, the patient will be discontinued from atezolizumab. However, atezolizumab may be withheld for > 12 weeks to allow for patients to taper off corticosteroids prior to resuming treatment. Atezolizumab can be resumed after being withheld for > 12 weeks if the Medical Monitor agrees that the patient is likely to derive clinical benefit. Atezolizumab treatment may be suspended for reasons other than toxicity (e.g., surgical procedures) with Medical Monitor approval. The investigator and the Medical Monitor will determine the acceptable length of treatment interruption.

Hu5F9-G4 treatment may be temporarily suspended in patients experiencing toxicity considered to be related to study treatment (see the Dose Modifications section). If a patient misses three or more consecutive doses during the combination treatment period, the investigator and Medical Monitor will decide whether the patient should discontinue Hu5F9-G4 permanently. If Hu5F9-G4 is withheld for > 28 days because of toxicity, the patient should be discontinued from Hu5F9-G4. However, if the investigator believes the patient is likely to derive clinical benefit and the Medical Monitor is in agreement, Hu5F9-G4 can be resumed after being withheld for > 28 days. If the time interval between Hu5F9-G4 doses is > 4 weeks on account of missed doses, a repriming period is required prior to restarting weekly doses. If repriming is necessary, atezolizumab should be held during the repriming week and restarted when the 30-mg/kg weekly dosing of Hu5F9-G4 begins.

If atezolizumab is discontinued, Hu5F9-G4 should also be discontinued. If Hu5F9-G4 is discontinued, atezolizumab can be continued if the patient is likely to derive clinical benefit, as determined by the investigator.

MANAGEMENT GUIDELINES

Guidelines for the management of patients who experience specific adverse events are provided in [Appendix 9](#) for atezolizumab-related adverse events and in the Atezolizumab Investigator's Brochure. This section integrates management guidelines for those adverse events when both atezolizumab and Hu5F9-G4 have developed guidance. This section also includes generic guidance for management of Hu5F9-G4.

Appendix 8

Overall Guidelines for Management of Patients Who Experience Adverse Events (cont.)

when atezolizumab-associated adverse events occur. This section includes management guidelines for Hu5F9-G4-associated adverse events. For cases in which management guidelines are not covered in [Appendix 9](#), the Hu5F9-G4 Investigator's Brochure, or the protocol, patients should be managed as deemed appropriate by the investigator according to best medical judgment.

INFUSION-RELATED REACTIONS AND ANAPHYLAXIS

Management guidelines for patients who experience infusion-related reactions or anaphylaxis are presented in [Table 1](#).

Table 1 Guidelines for Management of Patients Who Experience Adverse Events Associated with Hu5F9-G4

Event	Action to Be Taken
IRRs and anaphylaxis	
IRR, Grade 1	
Follow guidelines for atezolizumab in Appendix 9.For anaphylaxis precautions, see Appendix 7.
IRR, Grade 2	
Follow guidelines for atezolizumab in Appendix 9.For anaphylaxis precautions, see Appendix 7.For Hu5F9-G4:
Stop the Hu5F9-G4 infusion, begin an IV infusion of normal saline, and treat the patient with diphenhydramine 50 mg IV or equivalent and/or 500 to 750 mg oral paracetamol/acetaminophen.Remain at bedside and monitor patient until resolution of symptoms.Corticosteroid therapy may also be administered at the discretion of the investigator.If the infusion is interrupted, wait until symptoms resolve, then restart the infusion at 50% of the original infusion rate when symptoms resolve.If symptoms recur, then stop infusion and disconnect the patient from the infusion apparatus; no further Hu5F9-G4 will be administered at that visit. The amount of study drug infused must be recorded on the electronic Case Report Form.Patients who experience an infusion reaction of Grade 2 during the 4-hour post-infusion observation period that does not resolve during that time should be observed for 24 hours or until the adverse event resolves, with vital sign measurements every 4 hours and additional evaluations as medically indicated for the management of the adverse event.

IRR=infusion-related reaction.

Appendix 8
Overall Guidelines for Management of Patients Who Experience Adverse Events (cont.)

Table 1 Guidelines for Management of Patients Who Experience Adverse Events Associated with Hu5F9-G4 (cont.)

Event	Action to Be Taken
IRRs and anaphylaxis (cont.)	
IRR, Grade 3 or 4	
 • Follow guidelines for atezolizumab in Appendix 9. • For anaphylaxis precautions, see Appendix 7. • For Hu5F9-G4: 
 – Stop infusion and permanently discontinue Hu5F9-G4. – Begin an IV infusion of normal saline, and treat the patient as follows: administer bronchodilators, epinephrine 0.2 to 1 mg of a 1:1000 solution for SC administration or 0.1 to 0.25 mg of a 1:10,000 solution injected slowly for IV administration, and/or diphenhydramine 50 mg IV with methylprednisolone 100 mg IV or equivalent, as needed. – Administer aggressive symptomatic treatment. – All patients will be observed for an additional 24 hours or longer until the adverse event resolves, with vital sign measurements every 4 hours and additional evaluations as medically indicated for the management of the adverse event.
Atezolizumab-related toxicities not described above	
Grade 1 or 2	
 • Follow guidelines for atezolizumab in Appendix 9. • Continue Hu5F9-G4.
Grade 3	
 • Follow guidelines for atezolizumab in Appendix 9. • Continue Hu5F9-G4.
Grade 4	
 • Follow guidelines for atezolizumab in Appendix 9. • Hu5F9-G4 may be continued at the discretion of the investigator per medical judgment.

IRR=infusion-related reaction.

Hu5F9-G4-ASSOCIATED ANEMIA

Anemia, Blood Crosmatching, and Packed RBC Transfusion Procedures

Hu5F9-G4 binds to RBCs and leads to erythrophagocytosis. This, coupled with anemia from other cause in patients with cancers, means that care has to be taken with RBC crossmatching and packed RBC transfusions. There is a possibility that treatment with Hu5F9-G4 may obscure assessment of RBC phenotyping, although this has not been observed in patients to date.

Appendix 8

Overall Guidelines for Management of Patients Who Experience Adverse Events (cont.)

At baseline, prior to initiation of Hu5F9-G4 therapy, blood cell ABO phenotyping for minor antigens, type, and screen (ABO blood type and Rhesus [Rh] factor), and direct antibody testing (DAT) will be performed to facilitate, together with the prior phenotype, allocation of properly crossmatched blood in the event a blood transfusion is warranted.

For patients after exposure to Hu5F9-G4, ABO, Rh, and DAT may be pan-reactive because of Hu5F9-G4 binding to RBCs. Therefore, if a non-urgent transfusion is ordered by the investigator, perform the following procedures:

- Front type: EGA-treated cells ($\times 2$ maximum) and warm wash $\times 4$ (minimum) with 0.9% saline
- Back type: Perform reverse anti-human globulin for both A and B.
- If a valid ABO type cannot be obtained, mark the final report as invalid and notify the transfusion service for the site.
- Antibody screen

If a pan-agglutinin/warm autoantibody is present in low-ionic-strength solution, repeat the antibody screen with polyethylene glycol (PeG). Perform PeG adsorption studies and elution studies.

Blood Components for Transfusion

For all elective red cell transfusions, leukocyte-reduced units matched for the phenotype of the patients (as described above) will be used. Where exact matching for all specified blood groups proves impractical (e.g., for MNS), local sites will decide on the best-matched donor units to be used. Cytomegalovirus (CMV) matching (i.e., CMV-seronegative units for CMV-seronegative patients) will not be required for this study because it will limit the inventory for antigen matching.

If the crossmatch is incompatible, the RBC units that are Coombs crossmatched incompatible will be selected (e.g., phenotype matched or least incompatible) for issue at the discretion of the sites' transfusion Service Medical Director or equivalent person, where available.

Hu5F9-G4 Impact on Red Blood Cell Transfusion Procedures

Hu5F9-G4 binds to red cells and leads to erythrophagocytosis. This, coupled with anemia from other causes in patients with cancers, means that care has to be taken with RBC crossmatching and packed RBC transfusions. There is a possibility that treatment with Hu5F9-G4 may obscure assessment of RBC phenotyping, although this has not been observed in patients treated to date.

Appendix 8

Overall Guidelines for Management of Patients Who Experience Adverse Events (cont.)

During the screening period prior to initiation of Hu5F9-G4 therapy, blood cell ABO phenotyping for minor antigens, type and screen (ABO/Rh), and DAT will be performed for each patient. This, together with using the prior phenotype, will facilitate allocation of properly crossmatched blood in the event a blood transfusion is warranted.

For patients after exposure to Hu5F9-G4:

- ABO, Rh, and DAT may be pan-reactive owing to Hu5F9-G4 binding to red cells. Therefore, if a non-urgent transfusion is ordered by the investigator, perform the following procedures:
 - Front type: EGA-treated cells (approximately 2 maximum) and warm wash (approximately 4 minimum) with 0.9% saline.
 - Back type: Perform reverse anti-human globulin for both A and B.
 - If a valid ABO type cannot be obtained, mark the final report as invalid and notify the transfusion service for the site.
- Antibody screen:
If a pan-agglutinin or warm autoantibody is present in low ionic strength solution, repeat the antibody screen with polyethylene glycol (PeG). Perform PeG adsorption studies and elution studies.

For emergency transfusions, the transfusion laboratory may consider using emergency Group O Rh-negative units if the phenotyped units are not available.

Blood plasma therapy will be blood type specific. Platelets will be blood type compatible whenever possible, and if not, will have been tested and found not to have high-titer anti-A or anti-B.

Appendix 9

Risks Associated with Atezolizumab and Guidelines for Management of Adverse Events Associated with Atezolizumab

Toxicities associated or possibly associated with atezolizumab treatment should be managed according to standard medical practice. Additional tests, such as autoimmune serology or biopsies, should be used to evaluate for a possible immunogenic etiology.

Although most immune-mediated adverse events observed with immunomodulatory agents have been mild and self-limiting, such events should be recognized early and treated promptly to avoid potential major complications. Discontinuation of atezolizumab may not have an immediate therapeutic effect, and in severe cases, immune-mediated toxicities may require acute management with topical corticosteroids, systemic corticosteroids, or other immunosuppressive agents.

The investigator should consider the benefit–risk balance a given patient may be experiencing prior to further administration of atezolizumab. In patients who have met the criteria for permanent discontinuation, resumption of atezolizumab may be considered if the patient is deriving benefit and has fully recovered from the immune-mediated event. Patients can be re-challenged with atezolizumab only after approval has been documented by both the investigator (or an appropriate delegate) and the Medical Monitor.

MANAGEMENT GUIDELINES

PULMONARY EVENTS

Dyspnea, cough, fatigue, hypoxia, pneumonitis, and pulmonary infiltrates have been associated with the administration of atezolizumab. Patients will be assessed for pulmonary signs and symptoms throughout the study and will also have computed tomography (CT) scans of the chest performed at every tumor assessment.

All pulmonary events should be thoroughly evaluated for other commonly reported etiologies such as pneumonia or other infection, lymphangitic carcinomatosis, pulmonary embolism, heart failure, chronic obstructive pulmonary disease, or pulmonary hypertension. Management guidelines for pulmonary events are provided in [Table 1](#).

Appendix 9

Risks Associated with Atezolizumab and Guidelines for Management of Adverse Events Associated with Atezolizumab (cont.)

Table 1 Management Guidelines for Pulmonary Events, Including Pneumonitis

Event	Management
Pulmonary event, Grade 1	
 • Continue atezolizumab and monitor closely. • Re-evaluate on serial imaging. • Consider patient referral to pulmonary specialist.
Pulmonary event, Grade 2	
 • Withhold atezolizumab for up to 12 weeks after event onset.^a • Refer patient to pulmonary and infectious disease specialists and consider bronchoscopy or BAL. • Initiate treatment with corticosteroids equivalent to 1–2 mg/kg/day oral prednisone. • If event resolves to Grade 1 or better, resume atezolizumab.^b • If event does not resolve to Grade 1 or better while withholding atezolizumab, permanently discontinue atezolizumab and contact Medical Monitor.^c • For recurrent events, treat as a Grade 3 or 4 event.
Pulmonary event, Grade 3 or 4	
 • Permanently discontinue atezolizumab and contact Medical Monitor.^c • Bronchoscopy or BAL is recommended. • Initiate treatment with corticosteroids equivalent to 1–2 mg/kg/day oral prednisone. • If event does not improve within 48 hours after initiating corticosteroids, consider adding an immunosuppressive agent. • If event resolves to Grade 1 or better, taper corticosteroids over ≥ 1 month.

BAL = bronchoscopic alveolar lavage.

- ^a Atezolizumab may be withheld for a longer period of time (i.e., > 12 weeks after event onset) to allow for corticosteroids (if initiated) to be reduced to the equivalent of ≤ 10 mg/day oral prednisone. The acceptable length of the extended period of time must be agreed upon by the investigator and the Medical Monitor.
- ^b If corticosteroids have been initiated, they must be tapered over ≥ 1 month to the equivalent of ≤ 10 mg/day oral prednisone before atezolizumab can be resumed.
- ^c Resumption of atezolizumab may be considered in patients who are deriving benefit and have fully recovered from the immune-mediated event. Patients can be re-challenged with atezolizumab only after approval has been documented by both the investigator (or an appropriate delegate) and the Medical Monitor.

Appendix 9

Risks Associated with Atezolizumab and Guidelines for Management of Adverse Events Associated with Atezolizumab (cont.)

HEPATIC EVENTS

Immune-mediated hepatitis has been associated with the administration of atezolizumab. Eligible patients must have adequate liver function, as manifested by measurements of total bilirubin and hepatic transaminases, and liver function will be monitored throughout study treatment. Management guidelines for hepatic events are provided in [Table 2](#).

Patients with right upper-quadrant abdominal pain and/or unexplained nausea or vomiting should have liver function tests (LFTs) performed immediately and reviewed before administration of the next dose of study drug.

For patients with elevated LFTs, concurrent medication, viral hepatitis, and toxic or neoplastic etiologies should be considered and addressed, as appropriate.

Table 2 Management Guidelines for Hepatic Events

Event	Management
Hepatic event, Grade 1	
Continue atezolizumab.Monitor LFTs until values resolve to within normal limits or to baseline values.
Hepatic event, Grade 2	
All events:
 
Monitor LFTs more frequently until return to baseline values. 
Events of > 5 days' duration:
 
Withhold atezolizumab for up to 12 weeks after event onset.^aInitiate treatment with corticosteroids equivalent to 1–2 mg/kg/day oral prednisone.If event resolves to Grade 1 or better, resume atezolizumab.^bIf event does not resolve to Grade 1 or better while withholding atezolizumab, permanently discontinue atezolizumab and contact Medical Monitor.^c

LFT = liver function test.

^a Atezolizumab may be withheld for a longer period of time (i.e., >12 weeks after event onset) to allow for corticosteroids (if initiated) to be reduced to the equivalent of ≤ 10 mg/day oral prednisone. The acceptable length of the extended period of time must be agreed upon by the investigator and the Medical Monitor.

^b If corticosteroids have been initiated, they must be tapered over ≥ 1 month to the equivalent of ≤ 10 mg/day oral prednisone before atezolizumab can be resumed.

^c Resumption of atezolizumab may be considered in patients who are deriving benefit and have fully recovered from the immune-mediated event. Patients can be re-challenged with atezolizumab only after approval has been documented by both the investigator (or an appropriate delegate) and the Medical Monitor.

Appendix 9
Risks Associated with Atezolizumab and Guidelines for Management of Adverse Events Associated with Atezolizumab (cont.)

Table 2 Management Guidelines for Hepatic Events (cont.)

Event	Management
Hepatic event, Grade 3 or 4	
• Permanently discontinue atezolizumab and contact Medical Monitor.^c• Consider patient referral to gastrointestinal specialist for evaluation and liver biopsy to establish etiology of hepatic injury.• Initiate treatment with corticosteroids equivalent to 1–2 mg/kg/day oral prednisone.• If event does not improve within 48 hours after initiating corticosteroids, consider adding an immunosuppressive agent.• If event resolves to Grade 1 or better, taper corticosteroids over ≥ 1 month.

LFT = liver function test.

- ^a Atezolizumab may be withheld for a longer period of time (i.e., > 12 weeks after event onset) to allow for corticosteroids (if initiated) to be reduced to the equivalent of ≤ 10 mg/day oral prednisone. The acceptable length of the extended period of time must be agreed upon by the investigator and the Medical Monitor.
- ^b If corticosteroids have been initiated, they must be tapered over ≥ 1 month to the equivalent of ≤ 10 mg/day oral prednisone before atezolizumab can be resumed.
- ^c Resumption of atezolizumab may be considered in patients who are deriving benefit and have fully recovered from the immune-mediated event. Patients can be re-challenged with atezolizumab only after approval has been documented by both the investigator (or an appropriate delegate) and the Medical Monitor.

GASTROINTESTINAL EVENTS

Immune-mediated colitis has been associated with the administration of atezolizumab. Management guidelines for diarrhea or colitis are provided in [Table 3](#).

